2. SYNOPSIS

Study Title	A retrospective observational analysis of a cohort with Heart Failure with Preserved Ejection Fraction from a BNP pathway clinic
Problem statement	Heart failure with preserved ejection fraction (HFpEF) is a complex condition with various causes that is not yet fully understood. Most significantly there is no single method of diagnosing or treating the condition. Recently a novel non-invasive diagnostic criterion to predict the likelihood of HFpEF was proposed by Reddy et al. (2018) called H2FPEF. The main limitation of this study was the use of a single centre population from the Mayo clinic in Rochester, US. Another limitation is that the H2FPEF diagnostic criterion consists of common and often co-existing conditions which could as a result overestimate HFpEF probability. The aim of the investigators is to retrospectively test the H2FPEF criteria on the population at Queen Alexandra Hospital (QAH) in Portsmouth, which is of a lower socio-economic status and greater ethnic diversity. Implications of the project if H2FPEF is proved to be generalizable to the population is that it can be used within the Trust and rolled out to others. This would allow diagnosis to be made quicker and more cost effectively using echocardiography and without the need for invasive cardiac catheterisation. On the other hand if H2FPEF is found not to be applicable to the population then further research would be required to find the ideal diagnostic tool.
Research question / hypothesis	The investigator's hypothesis is that when H2FPEF criteria is compared against retrospectively held data for the patient population at QAH that this will overestimate the probability of HFpEF
Study Design	The study is a single-centre retrospective observational analysis
Study Participants	Patients who attended heart failure clinics at Queen Alexandra Hospital between January 1st 2016 – December 31st 2016
Planned Sample Size	2000
Follow-up duration	1 year
Planned Study Period	04/10/2019 – 30/04/2020
Primary Objective	The primary objective of the investigator's project is to test if the H2FPEF score accurately predicts HFpEF on the population at Queen Alexandra Hospital.

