Secondary Objectives	
 • Investigate if H2FPEF overestimates HFpEF diagnosis on the patient population when compared against known BNP levels. • To evaluate if H2FPEF can be validated on the patient population and be utilised to improve patient pathway for HFpEF. • To monitor patient responses to treatments and care for one year.
Primary Outcome Measure	To assess the predictive accuracy of H2FPEF at predicting HFpEF on the patient population as calculated by logistic regression, with diagnostic accuracy being assessed by sensitivity and specificity calculations.
Secondary Outcome Measures	
 • ANOVA will be performed to provide one simultaneous evaluation of the data to determine if there is a significant difference between

	H2FPEF score and diagnosis of HFpEF. •To assess number of hospital admissions and any changes in treatment/ care after one year for the population.
--	--

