4. LAY SUMMARY

Heart failure with preserved ejection fraction (HFpEF) is a complex condition with various causes that is not yet fully understood. Heart failure is a long-term condition where the heart is unable to pump enough blood to meet the demands of the body. Heart failure is then categorised based on ejection fraction, which is the percentage of how much blood the heart pumps out each beat. HFpEF is a form of heart failure where the heart still pumps >50% of its volume each heart beat. Most significantly there is no method of diagnosing or treating the condition. A recent project proposed non-invasive criteria using routinely collected data to predict the likelihood of HFpEF. This was termed H2FPEF and uses: weight, number of hypertensive medications prescribed, age, presence of atrial fibrillation, ventricular filling pressures and pulmonary hypertension. The main limitation of this study is the use of a single centre population from the Mayo clinic in Rochester, US. Another limitation is that the H2FPEF criterion consists of common conditions which could as a result overestimate HFpEF probability. The aim of the investigators is to test the H2FPEF criteria on previous data already held from heart failure clinic database at Queen Alexandra Hospital (QAH) in Portsmouth. Implications of the project if H2FPEF is proved to be accurate on the population is that it can be used within the Trust and other trusts. This would allow HFpEF to be identified quicker at a reduced cost for the trust and reduced risk for the patient avoiding invasive investigations. On the other hand if H2FPEF is found not to be applicable to the population then further research would be required to find the ideal tool or method to identify HFpEF. A follow-up of patients is also proposed to monitor any long-term outcomes and how they respond to treatments.

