5. BACKGROUND AND RATIONALE

Epidemiology:

In the UK heart failure is the biggest cause of hospital admissions in people aged over 65, and is associated with poor morbidity and mortality outcomes if not managed effectively (National Institute for Health Care and Excellence [NICE], 2015). Heart failure is a complex heterogeneous condition characterised by typical symptoms and signs indicative of structural or functional cardiac abnormalities which despite normal filling pressures results in failure to deliver oxygen at a rate proportionate to the demands of metabolizing tissues (Ponikowski et al., 2016). Typical symptoms of heart failure include shortness of breath, reduced exercise tolerance, fatigue, orthopnoea and paroxysmal nocturnal dyspnoea; with signs such as peripheral oedema, functional mitral regurgitation, murmur and elevated jugular venous pressure (Allen et al., 2015). All of these signs and symptoms are however not specific to heart failure and could be caused by alternative conditions which makes diagnosis difficult (Oren and Goldberg, 2017).

Heart failure is categorised based on ejection fraction (EF);

- EF <40% - Heart failure with reduced ejection fraction (HFrEF)
- EF 40-49% - Heart failure with mid-range ejection fraction (HFmrEF)
- EF ≥50% - Heart failure with preserved ejection fraction (HFpEF)

The aetiology of HFpEF is less well understood compared to HFrEF because it is not a uniform disease and patients usually have a combination of morbidities, but there is now a greater focus on it as it is just as prevalent (Lam et al., 2011; Dunlay et al., 2017; van Empel and Rocca, 2018). No effective therapies have as yet been found for management of HFpEF, with therapies that have proven effective in reducing mortality and morbidity in HFrEF patients not having the same effect for HFpEF patients, making this an important research focus (O’Gallagher and Shah, 2018). Approximately half of heart failure patients are now believed to have HFpEF, with the prevalence increasing and set to become the dominant form of heart failure as the condition becomes better understood and diagnosed (Banerjee, 2016; Deaton et al., 2018).

Background:

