HFpEF was previously characterised as ‘diastolic dysfunction’ but this terminology was changed as it was found that diastolic dysfunction was also seen in patients with ‘systolic dysfunction’ (Borlaug and Paulus, 2011). Myocardial stiffness which leads to increased filling pressures is a common pathophysiologic attribute of HFpEF despite its multifactorial aetiology (Telles and Marwick, 2018). Other common conditions associated with HFpEF include: atrial fibrillation (AF), chronotropic incompetence, pulmonary hypertension, right ventricular dysfunction and endothelial dysfunction; with common non-specific risk factors such as: age, gender, hypertension, obesity, diabetes, metabolic syndrome and renal failure (Borlaug, 2014; Ferrari et al., 2015; Harper et al., 2018). This complex heterogeneity of HFpEF which is not yet fully understood highlights the difficulty that clinicians have in being able to diagnose the condition.

Diagnosis of HFpEF is difficult and as of yet there is no test to confirm diagnosis, with current guidelines saying initial diagnosis should include the presence of typical signs and symptoms, an elevated B-type natriuretic peptide (BNP) (>35 pg/mL and/or N-Terminal pro-

B-type Natriuretic Peptide [NT-proBNP] >125 pg/mL) and ejection fraction $\geq 50\%$ (Lekavich et al., 2015; Ponikowski et al., 2016). Echocardiography is the preferred method of assessing for HFpEF due to it being widely available, non-invasive, and able to provide immediate results (Ponikowski et al., 2016). Recent studies comparing the use of echocardiography against 'gold standard' invasive cardiac catheterisation to assess cardiac filling pressures found echocardiography to be just as accurate and reliable (Anderson et al., 2017; Lancellotti et al., 2017). Implications of this research would be that patients could be assessed as outpatients by focus echocardiography rather than invasively in the cardiac catheterisation lab, which would improve patient experience, enhance patient outcomes and prove cost-effective for trusts.

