9.2 Overall Description of Study Participants

All participants will be patients who have attended heart failure clinics at QAH between 01/01/2016 – 31/12/2016. Eligibility will be met by the inclusion and exclusion criteria.

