11.4 Study Assessments

All data will be collected retrospectively from the heart failure clinic database at QAH. Data will be collected on: weight, number of hypertensive medications prescribed, presence of AF or not, presence of pulmonary hypertension or not, age and filling pressure. These are the factors that make up Reddy et al. (2018) H2FPEF score. In addition the patient's ejection fraction and BNP will also be recorded as a measure to determine HFpEF diagnosis. All data will be anonymised and recorded on a Microsoft Excel spreadsheet, with a separate document documenting the pseudonymised data. All data will have been routinely collected as part of the heart failure patient pathway:

- Echocardiography - A non-invasive ultrasound test which takes approximately 30 minutes and has no radiation risk. Echocardiogram results will be used to ascertain pulmonary pressure and diastolic filling pressure. This will have been performed routinely as part of the heart failure patient pathway at QAH. All scans will have been performed on GE Healthcare Vivid echocardiography machines by a trained sonographer from the Cardiac Investigations Unit at QAH. A standard operating procedure exists for performing echocardiogram. In accordance with local practice personal protective equipment is worn for this test. ECG electrodes and ultrasound gel can be a potential risk to the patient with regards to dermatological reaction/sensitivity, however both are hypoallergenic substances.
- 12-lead electrocardiogram (ECG) - A non-invasive test of the electrical conduction of the heart assessing heart rate and rhythm. ECG results will be used to determine if the patient is in AF or not. All ECG will have been recorded with the use of the hospitals standard machine (MAC 1200, GE Healthcare). All tests will have been

performed by trained staff within the Cardiac Investigations Unit at QAH. Standard operating procedures are followed to perform ECG. ECG will have been performed routinely as part of the heart failure patient pathway at QAH.

- Weight - Using a standard trust scale (Marsden Weighing Company, UK)
- Age and Number of hypertensive medications taken - Assessed from patient records

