13.2 Analysis of Outcome Measures

To determine if the H2FPEF score was accurate in predicting HFpEF the calculated H2FPEF score will be compared against BNP blood test results using the cut-off points stated by the European Society of Cardiology (Ponikowski et al., 2016). To test our hypothesis an analysis of variance test (ANOVA) will be performed to provide one simultaneous evaluation of the data to determine if there is a significant difference between H2FPEF score and diagnosis of HFpEF. A logistic regression analysis will then be carried out to give an odds ratio and provide a predictive analysis of the data. All statistical analysis will be performed using SPSS software.

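### The reference diagnosis is not settled: Section 13.2 uses BNP cut-offs alone, Section 11.4 uses EF and BNP, and no eligibility or analysis section applies an EF limit

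*Combined protocol and SAP*

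**What the plan says.** The primary outcome in the Synopsis is the predictive accuracy of H2FPEF for HFpEF, "with diagnostic accuracy being assessed by sensitivity and specificity calculations". Section 13.2 supplies the comparator: "the calculated H2FPEF score will be compared against BNP blood test results using the cut-off points stated by the European Society of Cardiology". EF is not mentioned anywhere in Section 13. The ANOVA sentence in 13.2 refers to the diagnosis of HFpEF without defining it. The question of overestimation (Synopsis, 7.2 and 8.2) is also set against BNP levels only.

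Section 11.4 says something different: the patient's "ejection fraction and BNP will also be recorded as a measure to determine HFpEF diagnosis". It gives no EF threshold and no rule for combining the two.

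The EF limit appears only in descriptive text. Section 5 lists "EF ≥50% - Heart failure with preserved ejection fraction (HFpEF") and puts EF <40% and 40-49% in the separate categories HFrEF and HFmrEF. It also describes "current guidelines saying initial diagnosis should include the presence of typical signs and symptoms, an elevated B-type natriuretic peptide (BNP") above 35 pg/mL and/or NT-proBNP above 125 pg/mL, together with EF ≥50%. The Lay Summary puts it as "HFpEF is a form of heart failure where the heart still pumps >50% of its volume each heart beat".

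On who is included, Section 9.2 says "All participants will be patients who have attended heart failure clinics at QAH" in 2016, subject to 9.3. Section 9.3 requires an echocardiogram and a BNP test but no EF value. Section 13.1 analyses all eligible patients alike. The form in 12.1 has no EF or BNP column, and 13.3 limits collection to score data.

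**The concern.** Sensitivity and specificity have meaning only against a stated reference diagnosis. Here the analysis section names one comparator (BNP), while the assessment section names another (EF and BNP). The defining limit, EF ≥50%, is not carried into any section that selects or analyses patients.

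The cohort comes from heart failure clinics, and Section 5 itself says that only about half of heart failure patients are believed to have HFpEF. Patients with EF <50% and raised BNP are therefore to be expected. Whether each one is a case, a non-case or outside the analysis affects the primary sensitivity and specificity, the ANOVA groups and the logistic regression outcome. It also bears on the study hypothesis, because overestimation is judged by how many score-positive patients are not HFpEF. If the rule is left open, it may be chosen after the data have been seen.

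**Working it through.** **Step 1: the sections side by side**

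| Section | What establishes HFpEF |
|---|---|
| 13.2, accuracy | BNP against ESC cut-offs |
| 13.2, ANOVA | diagnosis of HFpEF, undefined |
| Synopsis, 7.2, 8.2 (overestimation) | BNP levels only |
| 11.4 | EF and BNP, no limits, no combining rule |
| 5 | signs and symptoms, raised natriuretic peptide, EF ≥50% |
| 9.3 | echo and BNP must have been done; no EF limit |
| 12.1 | no EF or BNP column |
| 13.1 | no EF restriction |

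Take a patient with EF <50% and raised BNP. Under 13.2 read literally, the patient is a case. Under 11.4 read with Section 5, the patient is not HFpEF, but the documents do not say whether to leave the patient out or count a non-case. That gives three possible treatments of the same patient.

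**Step 2: illustration of size**

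The plan has no figure to reproduce. It gives no EF or BNP distribution, and Section 8.1 gives the score's points but no positivity cut-off. Apart from N = 2000 (Synopsis), every input is an assumption:
- 20% have EF <50%: 400 patients, against 1600 with EF ≥50%.
- BNP is raised in 95% of the 400 (380 raised, 20 not) and in 70% of the 1600 (1120 raised, 480 not).
- In EF ≥50%, sensitivity is 0.80 (0.80 × 1120 = 896 true positives) and specificity 0.70 (0.30 × 480 = 144 false positives).
- A share q of EF <50% patients score positive, whatever their BNP.

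Formulas:
- Sensitivity under 13.2 = (896 + 380q) / (1120 + 380) = 0.80 + (380/1500)(q − 0.80)
- Specificity under 13.2 = 1 − (144 + 20q) / (480 + 20)
- With EF <50% as non-cases, sensitivity stays 0.80 and specificity = 1 − (144 + 400q) / (480 + 400)
- In EF ≥50% only, sensitivity is 0.80 and specificity 0.70

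| q | Sensitivity, 13.2 | Specificity, 13.2 | Specificity, EF <50% as non-cases |
|---|---|---|---|
| 0.50 | 1086/1500 = 0.724 | 346/500 = 0.692 | 536/880 = 0.609 |
| 0.80 | 1200/1500 = 0.800 | 340/500 = 0.680 | 416/880 = 0.473 |
| 0.90 | 1238/1500 = 0.825 | 338/500 = 0.676 | 376/880 = 0.427 |

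Under 13.2, 380/1500 = 25% of the cases have EF <50%. The sign of the change in sensitivity is the sign of q − 0.80, so it can go either way.

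False positives among score-positives at q = 0.50:
- 13.2: 154/1240 = 12%
- EF ≥50% only: 144/1040 = 14%
- EF <50% as non-cases: 344/1240 = 28%

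Sensitivity under 13.2 at q = 0.50 for other EF <50% shares:
- 5%: (1064 + 47.5)/(1330 + 95) = 0.780
- 10%: (1008 + 95)/(1260 + 190) = 0.761
- 50%: (560 + 475)/(700 + 950) = 0.627

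The 50% line takes Section 5's statement about half of heart failure patients at face value. The exclusions in 9.3 may make the real share much lower.

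**The case against.** The best defence is that 13.2 only supplies the BNP threshold for a diagnosis that 11.4 already bases on EF and BNP. The ESC guideline cited in 13.2 is one of the sources Section 5 cites for a diagnosis that includes EF ≥50%, and the ANOVA sentence treats the diagnosis as something other than the BNP result. The study title fits this reading, since it speaks of "a cohort with Heart Failure with Preserved Ejection Fraction from a BNP pathway clinic". The exclusions for known structural heart disease and pre-existing cardiomyopathy would also remove some low-EF patients.

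Part of this stands: the intention may well be an EF-and-BNP diagnosis. But 11.4 gives no limit or combining rule, no text ranks it above 13.2, the title is not an eligibility criterion, and the exclusions are not EF criteria. Even on the defence's reading, an EF rule still has to be written.

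A reader might infer three stronger things that the documents do not support:
- That EF <50% patients will be counted as cases. This follows only if 13.2 is applied literally.
- That sensitivity will be understated. None of the score items in 8.1 is EF, and Section 5 calls them common and co-existing, so EF <50% patients could score positive as often as true cases or more often.
- That the 12.1 form and 13.3 make the EF-and-BNP diagnosis impossible. Section 11.4 expressly plans to record both, so these are drafting inconsistencies.

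**Conclusion.** The point holds as an unreconciled reference standard for the primary outcome, and it should be settled before data are extracted. Confidence is high on the inconsistency: the comparator stated in 13.2 differs from the diagnosis in 11.4 and Section 5, and no operative section applies an EF limit. The consequence, that HFrEF or HFmrEF patients are counted as HFpEF cases, is conditional on following 13.2 literally.

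Neither the size nor the direction is known. On the assumed rates, the change in sensitivity against an EF ≥50% analysis runs from −7.6 points through zero to +2.5 points as q goes from 0.50 to 0.90. Specificity under 13.2 changes little (0.69 against 0.70 at q = 0.50). The large contrast in specificity, 0.61 against 0.70 at q = 0.50, arises only if EF <50% patients are kept as non-cases. The case for the change rests on the undefined reference diagnosis and not on these figures.

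**What to change.** - **13.2:** replace the BNP-only comparator with one reference diagnosis that combines EF and natriuretic peptide, as 11.4 intends, at the protocol's own Section 5 limits: EF ≥50% plus BNP >35 pg/mL and/or NT-proBNP >125 pg/mL. Use it for both the accuracy and the overestimation analyses, and align the wording of the Synopsis, 7.2 and 8.2. Align the Lay Summary's >50% with ≥50%.
- **13.1:** state before data extraction whether EF <50% patients are left out or counted as non-cases, and report the other option as a sensitivity analysis. One workable choice is a primary analysis in EF ≥50% with the number removed reported. The documents require a stated rule, not this particular one.
- **Signs and symptoms:** either apply them to every patient in the same way or state that they are presumed from clinic referral. Using them only where they happen to be recorded would make the reference vary with record completeness.
- **12.1 and 13.3:** add EF and BNP/NT-proBNP columns, and reconcile 13.3 with 11.4.

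The cost is protocol wording and two spreadsheet columns. Echocardiography and BNP are already entry requirements, and 11.4 already plans to record EF and BNP. The downside is that, if EF <50% patients are left out, the analysed number may fall below 2000, possibly with few reference-negatives (1600 and 480 in the illustration).

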The main outcome of this project will be whether the H2FPEF score is able to accurately predict HFpEF on the patient population of QAH, Portsmouth or if it overestimates diagnosis. If the investigator's research hypothesis is accepted then future research will be required to either optimise H2FPEF score or to develop new HFpEF diagnostic criteria. The enigma of HFpEF would continue to be the focus of research with the aim of developing an applicable clinical diagnostic tool. Alternatively if the investigators accept the null hypothesis then the H2FPEF score will have been validated on the population and would have the potential to be used by QAH and other trusts. Future research would then be required on other populations to further assess the generalisability of H2FPEF. The implications of this would be that patients are able to be diagnosed with HFpEF quicker and non-invasively requiring just an ECG, a focus echocardiogram and a routine clinical examination. Consequently invasive

cardiac catheterisation would not be required for diagnosis which would improve patient outcomes and patient service experience, as well as being cost-effective for the trust.

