7.2 Secondary Objectives

The investigator's secondary objectives are to:

- Investigate if H2FPEF overestimates HFpEF diagnosis on the patient population when compared against known BNP levels.
- To evaluate if H2FPEF can be validated on the patient population and be utilised to improve patient pathway for HFpEF.
- Follow patients up over one year to monitor outcomes

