8.2 Primary and Secondary Outcome Measures

Primary outcome measure

- Accuracy of H2FPEF at predicting HFpEF on the patient population will be assessed as specificity and sensitivity as calculated by logistic regression

Secondary outcome measure

- Investigate if H2FPEF overestimates HFpEF diagnosis on the patient population when compared against known BNP levels.
- To evaluate if H2FPEF can be validated on the patient population and be utilised to improve patient pathway for HFpEF.
- To assess patient outcomes after one year, including any changes in medication or treatment as well as number of hospital admissions and reported symptoms.

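### H2FPEF is judged by sensitivity and specificity against a BNP-based reference that the protocol does not regard as confirmatory, so reference error alone could make the score seem to over- or under-diagnose, or could hide real overestimation

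*Combined protocol and SAP*

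**What the plan says.** Section 13.2 sets the comparison: "the calculated H2FPEF score will be compared against BNP blood test results using the cut-off points stated by the European Society of Cardiology". Section 11.4 describes the reference differently, saying that "the patient's ejection fraction and BNP will also be recorded as a measure to determine HFpEF diagnosis". One section thus uses BNP alone and the other EF plus BNP; both are BNP-based.

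The primary outcome in section 8.2 reads: "Accuracy of H2FPEF at predicting HFpEF on the patient population will be assessed as specificity and sensitivity as calculated by logistic regression". The Synopsis hypothesis is that, on this hospital's data, "this will overestimate the probability of HFpEF". Section 7.2 adds the objective "Investigate if H2FPEF overestimates HFpEF diagnosis on the patient population when compared against known BNP levels".

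Section 5 is cautious about the reference. It states: "Diagnosis of HFpEF is difficult and as of yet there is no test to confirm diagnosis". It then describes an initial diagnosis with three parts: symptoms and signs, a raised natriuretic peptide (BNP above 35 pg/mL and/or NT-proBNP above 125 pg/mL), and EF of at least 50%. Under Impact, the same section gives the main outcome as "whether the H2FPEF score is able to accurately predict HFpEF on the patient population of QAH, Portsmouth or if it overestimates diagnosis". If the hypothesis is accepted, the score is to be optimised or new criteria developed. If the null is accepted, the score counts as validated and could be used at this and other trusts.

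Sections 13.1 to 13.4 contain no composite or adjudicated reference, no analysis of reference error, and no stated limitation on this point.

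**The concern.** Sensitivity and specificity measure accuracy only when the reference is taken as the truth. A patient positive on the score and negative on the reference then counts against the score, although the reference may have missed the disease. A patient negative on the score and positive on the reference counts as a miss, although the peptide may be raised for another reason. The protocol's own background leaves both possibilities open.

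At stake is the meaning of either headline result. 'Overestimates' could come from a reference that misses cases. 'Validated' could come from a reference so non-specific that it conceals over-diagnosis. A large sample does not help: it narrows the interval around a biased comparison. The planned size is 2000, and the result is meant to inform adoption at the Trust and beyond.

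**Working it through.** The documents contain no accuracy or power calculation to reproduce, only the planned size of 2000. They also give no prevalence and no accuracy for the reference. The values below are assumptions chosen to show how the comparison behaves.

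**Set-up.** Let p be true prevalence, and Se and Sp the sensitivity and specificity of the BNP-based reference. Suppose H2FPEF makes no errors, so the score-positive fraction is p. Then:

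- reference-positive fraction = p·Se + (1−p)(1−Sp)
- apparent sensitivity = p·Se / [p·Se + (1−p)(1−Sp)]
- apparent specificity = (1−p)·Sp / [(1−p)·Sp + p(1−Se)]
- apparent net overestimate = p(1−Se) − (1−p)(1−Sp)

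**A perfect score, reference Se 0.70 and Sp 0.60 (assumed).**

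| p | Score positive | Reference positive | Difference | Apparent sensitivity | Apparent specificity |
|---|---|---|---|---|---|
| 0.7 | 70% | 0.49 + 0.12 = 61% | +9 points | 0.49/0.61 = 80% | 0.18/0.39 = 46% |
| 0.5 | 50% | 0.35 + 0.20 = 55% | −5 points | 0.35/0.55 = 64% | 0.30/0.45 = 67% |
| 0.3 | 30% | 0.21 + 0.28 = 49% | −19 points | 0.21/0.49 = 43% | 0.42/0.51 = 82% |

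The sign changes where 0.30p = 0.40(1−p), that is p = 0.40/0.70 = 0.57. Above that prevalence the perfect score appears to overestimate; below it, to underestimate.

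**No net difference.** With p = 0.5 and Se = Sp = 0.80, score and reference each label 50%, yet apparent sensitivity and specificity are both 0.40/0.50 = 80%.

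**Range.** Over p from 0.3 to 0.7, Se from 0.70 to 0.95 and Sp from 0.60 to 0.90, a perfect score shows:

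- apparent specificity from 0.18/0.39 = 46% to 0.63/0.645 = 98%
- apparent sensitivity from 0.21/0.49 = 43% to 0.665/0.695 = 96%

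**Real overestimation hidden.** Take p = 0.5, Se 0.95, Sp 0.60. The reference labels 0.475 + 0.20 = 67.5% positive. A score with sensitivity 1 and specificity 0.70 labels 0.50 + 0.15 = 65%. It over-diagnoses (65% against a true 50%) but labels fewer patients than the reference.

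**Effect of sample size.** With 2000 patients, p = 0.5, Se 0.80 and Sp 0.90, a perfect score gives 2000 × 0.5 × 0.20 = 200 apparent false positives and 2000 × 0.5 × 0.10 = 100 apparent false negatives. A paired (McNemar) comparison, used here only as a yardstick, gives z = 100/√300 = 5.8. With Se 0.90 and Sp 0.60 the counts are 100 and 400, and z = −300/√500 = −13.4. Reference error alone produces a strong signal in either direction.

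**The case against.** The case for leaving the plan alone has substance.

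- The reference uses guideline cut-offs, the data are routine clinic records, and neither catheterisation nor an adjudicated diagnosis is among the data listed. An imperfect reference is hard to avoid here. That stands, which is why no new reference test is asked for.
- The overestimation objective in section 7.2 is already worded relative to BNP levels. That stands for the objective, but the qualifier is missing from the primary outcome in section 8.2, from the Synopsis hypothesis and from the Impact text.
- Percent agreement is arithmetically the same as sensitivity and specificity. True; the new label changes what may be concluded, not the numbers.
- The ANOVA in section 13.2 does not count errors. Correct; the error-counting comes from the primary outcome.

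Three stronger readings are tempting and go too far. A reader might infer that the plan expressly counts every disagreement as an error of the score. It does not: no positivity threshold is given for a score that can reach 2+1+3+1+1+1 = 9, so the two-by-two table is implied by the named outcome, not specified. A reader might take the Impact text for a formal decision rule that would make the Trust reject a valid score. It is a narrative, and its stated consequence is further research. A reader might also infer that the bias favours the investigators' hypothesis. The table above shows it can run either way, and the documents do not say which is likelier.

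**Conclusion.** The concern holds in a limited form. The protocol says no test confirms HFpEF, then treats a BNP-based classification as the truth for its primary outcome and draws conclusions about the score itself, with no allowance for reference error. An accurate score could look as if it over- or under-diagnoses, and real overestimation could be masked.

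Neither the size nor the direction can be determined from the documents. Under the assumed reference accuracy of 0.70/0.60, the distortion for a perfect score runs from 9 points too many (at 70% prevalence) to 19 points too few (at 30%). These figures show sensitivity to the assumptions; they do not predict the study's result. What follows firmly is that the planned analysis can support a statement about agreement with the BNP-based classification. It cannot alone support 'overestimates HFpEF' or 'validated'. This should be corrected before analysis, but it does not invalidate the study.

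**What to change.** 1. Reconcile sections 11.4 and 13.2 to a single EF-plus-BNP reference. Make sure both items are captured: the collection form in section 12.1 has no column for either, and section 13.3 limits collection to data for the score.
2. State the H2FPEF threshold (or thresholds) for a positive result before analysis. Without one the two-by-two counts cannot be formed.
3. In sections 8.2 and 13.2, report positive and negative percent agreement with the EF-plus-BNP classification.
4. In the Impact text of section 5, replace 'overestimates' with a statement that the score classifies more (or fewer) patients as HFpEF than EF plus BNP does, and 'validated' with a statement that it agrees with EF plus BNP.
5. Add a supportive sensitivity table over a range of reference sensitivity and specificity, with the range justified. State the assumption about dependence between score errors and reference errors. Omit infeasible cells, for example those where the observed reference-positive fraction exceeds the assumed sensitivity, since the implied prevalence then exceeds 1 (for Se + Sp above 1). Do not make the conclusion depend on every cell agreeing: such a rule would turn on arbitrary limits.

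The cost is some rewording, one pre-stated threshold, two data columns and one extra table. The headline conclusion becomes more cautious.
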